A key outcome measure of this phase II study is the safety and tolerability of pulsed ACTH compared to placebo. Little background information on adverse effects of pulsed ACTH in MS is available. A preliminary report of a one-year study (17) reported generally no increase in adverse effects in MS subjects receiving pulsed ACTH compared to pulsed MP, and fewer "psychiatric episodes" in the ACTH group. Potential AEs of concern are primarily those related to corticotropin effects, i.e. common steroid-related AEs such as increased risk of infection, weight gain, glucose intolerance, osteoporosis, hypertension, fluid retention, electrolyte derangements, and mood or behavioral changes.

Safety and tolerability of ACTH will be assessed in three ways: via volunteered responses from subjects regarding AEs, by elicited responses regarding specific symptoms, and by laboratory and physical exam measures. The advantage of volunteered (unsolicited) responses is that they allow unexpected AE's to be assessed and tend to highlight more serious or distressing AEs, while elicited responses have the advantage of more sensitive detection of specific AEs of interest (32). The volunteered responses will be obtained by an investigator or study coordinator at each follow-up visit, asking the

subject "Have you had any medical problems since your last visit?" Responses will be recorded on a log and severity will be rated according to the Common Terminology Criteria for Adverse Events (CTCAE) version 4.03. Subjects may also report AE's by phone, and these will be rated and logged in a similar manner. Study personnel will contact subjects monthly (by phone, email, etc.) around the time of their scheduled study drug injections, to remind them of the injections and to check for any new AE. If a phone-reported AE is deemed serious or possibly serious, an unscheduled visit will be arranged to allow the local investigator to assess the AE more fully (see section 7E, Unscheduled Study Visits). Elicited responses will be assessed through a questionnaire that will explore insomnia, irritability, dyspepsia, injection pain, edema, dysgeusia, fatigue, vision, skin changes, and changes in menstruation.

Physical exam and laboratory measures will include objective measurements of weight, blood pressure, skin changes, edema, myopathy, cataracts, glucose, electrolyte abnormalities, bone mineral density (DEXA) and hepatic toxicity.

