The following events are considered protocol-defined AEs and should be recorded on the AE log:

1. Weight gain: 5% increase compared to baseline
2. Increased blood pressure: increase of >20mm systolic or 10mm diastolic compared to baseline
3. Increased A1c: absolute increase of 1% or greater from baseline (Screening visit value) that is sustained across 2 consecutive measures
4. Hypokalemia: any potassium value below the lower limit of normal
5. New Osteopenia (compared to Baseline): DEXA T score between -1 and -2.5
6. Osteoporosis: DEXA T score less than -2.5
7. A DEXA T score drop of ≥ -0.5 during the study

As is typical, the study will not be powered based on safety and tolerability measures because AEs are anticipated to be rare and because the type and severity of AEs may be unpredictable. **The main secondary endpoint for safety and tolerability will be a comparison of the number of serious adverse events (SAE) over the study period in the ACTH group versus the placebo group.** A SAE will be considered any event with a score equal or greater than 3 on the Common Terminology Criteria for Adverse Events (CTCAE) version 4.03. AEs receiving a mild or moderate grade will also be compared between the two treatment groups.

C. Cognition

Cognitive dysfunction is ubiquitous in MS, affecting an estimated 40-70% of patients (33), and is a major cause of disruption in daily and occupational function in MS patients (34). The most common domains of cognitive impairment in MS are memory, processing speed, visuospatial functions, verbal abilities, sustained attention and

executive function (35). The BRB-N is a set of five cognitive tests developed by National MS Society's Cognitive Function Study Group as a research tool to detect cognitive changes in MS patients and to evaluate the effect of treatment interventions on cognition (36). The five neuropsychological tests comprising the BRB-N were chosen for their ability to assess the cognitive domains most frequently impaired in MS in a practical time period (20-30 minutes). The BRB-N includes the Selective Reminding Test (SRT, a test of verbal learning and delayed recall), the 10/36 Spatial Recall Test (10/36, visuospatial learning and delayed recall), the Symbol Digit Modalities Test (SDMT, sustained attention and processing speed), the Paced Auditory Serial Addition Test (PASAT, sustained attention and processing speed) and Word List Generation task (WLG, verbal fluency).

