The possibility of mid-study therapy regimen change for some subjects (see Exclusion criteria g. and h.) will be accounted for in analysis by running models with and without these subjects to explore the impact of these changes on analysis results. If results from the two models are consistent, all subjects will be included in the final model.

There are multiple distinct outcomes of interest in this study; since each outcome measures a unique aspect of MS progression no adjustment for multiple comparisons is planned.

Primary endpoint:

Between group differences in the odds of a 20% or greater increase in T25FW, the primary outcome measure of clinical progression of MS, will be tested at 36 months using multiple logistic regression models adjusted for covariates. Generalized

estimating equation (GEE) models will be used to test for between group differences in change over time in clinical progression (20% or greater increase in T25FW) adjusted for covariates. To test for between group differences in time to clinical progression distribution curves, Cox proportional hazards models (conditional on model assumptions being met) or Kaplan-Meier analysis will be used.

Secondary endpoints:

Safety and tolerability

To evaluate safety and tolerability of ACTH, lists and descriptive statistics of adverse events, serious adverse event, and treatment compliance will be compiled and calculated for each group at each visit. Fisher's exact tests will be used to test for between group differences in specific adverse event rates, serious adverse event rates, and treatment compliance rates.

Between group differences in mean changes in physical exam and laboratory measures (weight, blood pressure, HgbA1c, bone mineral density) will be tested using two-sample t-tests. In addition, between group differences in the proportion of subjects with abnormal blood pressure, HgbA1C, electrolyte and bone mineral density levels will be tested using Chi-square tests or Fisher's exact tests.

Change in ambulation, cognition, and global measures of MS-related disability scores

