Safety data will be reviewed by the DSMB at 6 and 12 months and then annually, starting from the time the first subject receives a dose of study medication and ending at participant study completion (i.e., no active participants on study drug and enrollment closed). Reports from all DSMB meetings will be forwarded to the Institutional Review Board (IRB). Any SAEs or unexpected AE's reported at other times will be reviewed by the head of the DSMB and reported to other members of the DSMB if considered significant enough to warrant interim review by the full committee. In the event of unanticipated SAEs that reflect new or increased risk to the subjects and are considered possibly related to the study medication or procedures (UPIRTSO) the funding sponsor and all study sites will be notified within 48 hours of the local investigator learning of the event. The local IRB will be notified within that IRB's policy timelines (e.g., the University of Minnesota IRB will be notified within 10 business days). A detailed analysis of all AEs will be conducted at the end of the first year of the study. The efficacy measures will also be analyzed annually throughout the study to see whether any signal of benefit is appearing. However, the study will be terminated only if there are unacceptable adverse events, not because of lack of any efficacy signals since it may take the entire 3 year duration of the study for any

beneficial effect to become manifest. Study termination due to safety concerns will be at the discretion of the DSMB; no pre-specified stopping rules will be used.

8. Cytokine sub-study

There are multiple mechanisms by which melanocortins such as adrenocorticotrophic hormone (ACTH) might alter the course of multiple sclerosis (MS) in a beneficial way (16, 54). One such mechanism is altering the balance between pro-inflammatory and anti-inflammatory cytokines via direct immunomodulating effects of melanocortins on immune system cells. A sub-study will be performed (at the University of Minnesota site only) to evaluate the change in plasma cytokine levels in subjects receiving ACTH compared to those receiving placebo, in order to better elucidate the possible mechanisms of ACTH in MS.

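### SAEs are defined by CTCAE severity grade alone, so the main safety endpoint counts severe rather than serious events, and the 48-hour notice excludes serious events graded below 3

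*Combined protocol and SAP*

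**What the plan says.** All references are to the combined protocol and SAP.

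- **Definition (section 5.B, Safety and Tolerability).** "A SAE will be considered any event with a score equal or greater than 3" on CTCAE version 4.03. This is the only SAE definition in the plan.
- **What the score measures (section 5.B).** For adverse events that subjects report, "severity will be rated according to the Common Terminology Criteria for Adverse Events (CTCAE) version 4.03".
- **Endpoint (section 5.B).** The main secondary endpoint for safety is "a comparison of the number of serious adverse events (SAE) over the study period in the ACTH group versus the placebo group". For the remaining events, "AEs receiving a mild or moderate grade will also be compared between the two treatment groups".
- **Analysis (section 6.E, Safety and tolerability).** Fisher's exact tests are planned for "between group differences in specific adverse event rates, serious adverse event rates, and treatment compliance rates".
- **Review between DSMB meetings (section 7.G, Data Safety Monitoring).** SAEs, and also unexpected AEs with no grade limit, that are "reported at other times will be reviewed by the head of the DSMB".
- **48-hour notice (section 7.G).** The funding sponsor and all sites are told within 48 hours of an SAE that is unanticipated, signals a new or greater risk and may be related to the study drug or procedures.
- **Unscheduled visits (sections 5.B and 7.E).** "If a phone-reported AE is deemed serious or possibly serious, an unscheduled visit will be arranged". Section 7.E leaves the decision to the local investigator.

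**The concern.** Severity and seriousness are different properties of an event. Severity is how intense the event is. Seriousness is what it led to, for example death, a threat to life, admission to hospital or lasting disability. The plan uses a severity score to decide seriousness, so the two sets of events need not be the same.

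This matters here for two reasons. Section 6.B names safety and tolerability over three years as the main objective of the study, and the SAE comparison is its leading safety endpoint. Section 7.G sets no stopping rules in advance and leaves termination for safety to the DSMB's discretion. That discretion depends on events being classified correctly and reaching the right people in time.

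**Working it through.** No arithmetic applies: the plan states no figure that depends on the SAE definition, and section 5.B says that the study is not powered on safety. The check traces each use of SAE or serious from the definition to the rules that rely on it. For each rule it asks whether an event graded below 3 with a serious consequence can qualify.

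| Rule | Section | What must be true | Can such an event qualify? |
|---|---|---|---|
| SAE endpoint | 5.B | CTCAE score of 3 or more | No |
| Fisher's exact test on SAE rates | 6.E | Same SAE definition | No |
| 48-hour notice | 7.G | An SAE that is unanticipated, signals new or greater risk and is possibly related | No |
| Review by head of DSMB between meetings | 7.G | An SAE, or an unexpected AE of any grade | Yes if unexpected; no if expected |
| Unscheduled visit after a phone report | 5.B | Judged serious or possibly serious | Yes, by judgement |
| Unscheduled visit | 7.E | Judged potentially serious, possibly drug-related, or in need of in-person assessment | Yes, by judgement |
| AE log, comparison of mild and moderate AEs, scheduled DSMB review | 5.B, 6.E, 7.G | Any AE | Yes |

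Three steps follow.

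1. **Endpoint.** Section 5.B says that the score rates severity, and no section adds a consequence criterion. Grade alone therefore decides membership of the SAE count, and section 6.E carries the same set of events into its test.

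2. **48-hour notice.** The SAE label is necessary but not sufficient. An unanticipated, possibly related event that signals new risk still fails the rule as written if its grade is below 3.

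3. **Head of the DSMB.** The limb for unexpected AEs covers part of the gap. What remains is the expected event of lower grade with a serious consequence. Section 5.B already lists infection, fluid retention and mood or behavioural change among the steroid-type effects of concern. If the trial treats these as expected (an assumption, since the plan does not define the term), a lower-grade case with a serious consequence meets neither limb. Scheduled reviews fall at 6 and 12 months after the first dose in the trial and annually after that. Between the reviews at months 12 and 24, such a case could wait up to 24 − 12 = 12 months for the full DSMB.

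**The case against.** The strongest reply is that little is lost. Lower-grade AEs are logged, compared between arms and available at every scheduled DSMB review, and section 7.G adds a detailed analysis of all AEs at the end of the first year. Unexpected AEs of any grade go to the head of the DSMB. An event that met the other conditions of the 48-hour notice would probably be unexpected, and so would reach the DSMB head anyway. A count of grade 3 or higher events is also clear and reproducible, so part of the defect is its label.

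Most of this stands, and it limits the point. It does not remove it: the endpoint is still named for one kind of event and counts another, and the funding sponsor and sites still have no 48-hour notice of a lower-grade serious event.

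A reader might infer more from the definition than the documents support:

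- **That every safety trigger runs on grade.** It does not. Unscheduled visits rest on the investigator's judgement, and section 7.E admits possibly related events and events needing in-person assessment whatever their grade. What can be said is that serious has no definition there other than the grade rule in section 5.B.
- **That serious events of lower grade go unrecorded or bypass the DSMB.** They are recorded and reviewed. Only the expected ones miss review by the DSMB head between meetings.
- **That isolated blood-pressure, potassium or HbA1c readings will swell the SAE count.** The definition would admit any such reading graded 3 or higher. The plan does not reproduce the CTCAE grade descriptions, so the documents cannot show how often this would happen, or whether it could happen without clinical consequence. For the same reason they cannot show which admissions to hospital would be graded below 3.

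**Conclusion.** The point holds in a limited form. Because SAE is defined by severity grade only, the main safety endpoint and its test count severe events. A serious event graded below 3 is shut out of that count and of the 48-hour notice and, if expected, of review by the DSMB head between meetings. The harm is misclassification and lost expedited notice.

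The size cannot be computed. The documents give no AE rates by grade or by consequence, so the overlap between grade 3 or higher and a serious consequence is unknown. If the two sets coincided in practice, nothing would change. The conclusion rests on reading section 5.B as the definition for every later use of SAE, which is reasonable because the plan offers no other. It does not rest on any particular content of the CTCAE grades.

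**What to change.** 1. In section 5.B, rename the grade 3 or higher count severe AEs and keep it as a severity comparison.
2. In the same section, define an SAE by the consequence of the event, whatever its grade, and list the qualifying consequences.
3. Apply that definition to the SAE test in section 6.E and to the review and notification rules in section 7.G. Sections 5.B and 7.E can then use the same meaning when an event is judged for an unscheduled visit.
4. Add a seriousness field to the AE log, separate from the CTCAE grade, and report both counts by arm.

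The cost is protocol wording and one extra AE-log field. The SAE count may contain fewer events than the grade-based count, which would make that comparison less informative. The present count is kept under its new name, so no information is lost.

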Each subject will have OCT performed on each eye at baseline and then annually for 3 years (total of 4 OCT per subject). OCT will be performed on the Spectralis OCT system (Heidelberg Engineering, Germany) using the glaucoma protocol set. If the study center's available Spectralis OCT system has the neurology-oriented "N-site" software, then the RNFL scan (see below) will be obtained twice, once using the glaucoma protocol set and once using the axonal (N-site) protocol set. Pupillary dilation will not be routinely performed, as it is usually unnecessary for OCT (49). If dilation is deemed necessary to achieve adequate OCT quality (e.g., due to cataract), the subject may be excluded from the OCT portion of the study. Alternatively, dilation may be performed (with typical mydriatic eye drops) if the dilation and OCT are done after the other functional study assessments (e.g. EDSS, MSFC, LCVA, BRB-N) during the study visit, or if dilation/OCT are done on a separate visit day within a +/- 2 week window of other efficacy measures. In other words, pupillary dilation for OCT purposes will not be allowed to interfere with the other efficacy assessments that require vision for their performance.

Up to three different scans will be performed on each eye at each visit, to assess RNFL thickness, macular volume, and individual retinal layer thickness (ganglion cell layer, inner nuclear layer, etc). The RNFL scan will be obtained twice (once using the glaucoma protocol and once using the axonal protocol) if the axonal protocol is available. The axonal protocol (N-site) is optimized for detecting abnormalities in MS, and is thus the preferred method. However, all of the study sites are not expected to have access to the axonal protocol, while all will have the glaucoma protocol available. Therefore, we will obtain all scans on the glaucoma protocol (to ensure consistency of data), and acquire the axonal protocol RNFL scan as well when it is an option. The scans to be obtained are:

- i. **RNFL scan (circle scan)** – Standard settings for peripapillary RNFL with the Spectralis glaucoma protocol will be used: 12 degree (3.45 mm) circular scan manually centered on the optic disc, ART = 100, circle = 12°, 768 A-scans.
- ii. **Macular volume scan (posterior pole scan)** – The posterior pole scan from the glaucoma protocol set will be used, again using the standard settings: 30x25, 61 sections, 760 A-scans per section, distance between B-scans = 120 μ m, ART = 9.

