- iii. **(optional) RNFL scan (circle scan) using N-site software** – Standard settings for peripapillary RNFL with the Spectralis axonal protocol will be used: 12 degree (3.45 mm) circular scan manually centered on the optic disc, ART = 100, circle = 12°, 768 A-scans.

For each scan, minimum quality score is 20 (with a goal quality score of \geq 25). If a quality score of \geq 20 cannot be obtained, data from that scan will not be included for analysis. The individual centers/technicians obtaining the OCT will evaluate only for quality of the OCT scans (i.e., no

formal clinical interpretation of the OCT results will be performed. The image alignment eye-tracking system (TruTrack, Heidelberg Engineering, Germany) will be utilized throughout.

Data submitted from each OCT session will include printouts of all RNFL scans, plus electronic files (.e2e format) containing each of the 2 (or 3) scans.

If a study site does not have access to the Spectralis OCT system, a different spectral-domain high-resolution OCT system such as Cirrus HD-OCT (Zeiss) may be used as an alternative, with similar scans acquired (RNFL scan, macular volume/posterior pole).

Change in thickness of the temporal quadrant peripapillary RNFL over the course of the study will be a secondary study endpoint. Exploratory endpoints will include changes in macular volume and changes in other RNFL regions (e.g. superior, inferior, nasal, and global).

6. Statistical Issues and Data Analysis

A. Study Design

The study design is a randomized, double-blind, placebo-controlled, multi-center, phase II clinical trial.

B. Sample Size Calculation

The main objective of the study is to investigate the safety and tolerability of pulsed ACTH in progressive MS patients over three years. The primary efficacy endpoint of the study is the proportion of subjects exhibiting a 20% increase (worsening) from baseline in the T25FW. No baseline data are available regarding the rate at which a pooled population of progressive MS (i.e., SPMS, PPMS and/or PRMS) patients experience 20% increase in T25FW. However, Bosma et al. (53) evaluated change over 2 years in all three components of the MSFC (T25FW, 9HP, and PASAT) in 191 PPMS patients, and found that 45% of patients showed a 20% or greater increase in T25FW. This data was used as the basis for sample size considerations, with the following assumptions:

The findings in PPMS patients (53)

1. will generalize to a mixed sample of any progressive MS phenotype.

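### The OCT quality cut-off of 20 names no instrument although a second maker's system is allowed, and RNFL data from different systems would be pooled with no device or site term (minor)

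*Combined protocol and SAP*

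**What the plan says.** Section 5.G makes one instrument the default: "OCT will be performed on the Spectralis OCT system (Heidelberg Engineering, Germany) using the glaucoma protocol set". It wants every scan on that protocol set so that the data are consistent, and says of the sites that "while all will have the glaucoma protocol available".

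After listing the scans and their settings, it gives the inclusion rule: "For each scan, minimum quality score is 20", with a goal of 25 or more. If a score of 20 "cannot be obtained, data from that scan will not be included for analysis". The local operators apply it: "The individual centers/technicians obtaining the OCT will evaluate only for quality of the OCT scans". The next sentence is specific to one maker: "The image alignment eye-tracking system (TruTrack, Heidelberg Engineering, Germany) will be utilized throughout".

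The section then provides a fallback. Where a site has no Spectralis, "a different spectral-domain high-resolution OCT system such as Cirrus HD-OCT (Zeiss) may be used as an alternative". Similar RNFL and macular scans are asked for. No quality measure, threshold or conversion is given for such a system.

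Change in temporal-quadrant RNFL thickness is a secondary endpoint (5.G) and the measure behind hypothesis 5 (section 3). Section 6.E analyses it by linear regression adjusted for baseline thickness and other covariates, and by mixed models. The named covariates are age, gender and MS phenotype, with EDSS and disease duration added if significant. Neither device nor site is among them.

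**The concern.** The cut-off decides which scans enter the RNFL analysis. Read literally, it governs an instrument that it does not seem to have been written around. Read as a Spectralis rule, it leaves the permitted alternative with no criterion at all. In either case each site would have to settle the matter for itself, because section 5.G describes no central quality check.

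Two related gaps concern pooling. Nothing requires a subject's four scans (baseline and months 12, 24 and 36) to come from one system, so a change of instrument would put any difference between systems into that subject's change score. And even if each subject stays on one system, the models pool baseline thickness and change across instruments with no term to absorb a difference between them.

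At stake are the precision of one secondary endpoint and of the exploratory macular-volume measure, which falls under the same rule.

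**Working it through.** **1. The plan's own figure.** The only sample-size calculation (section 6.B) is for the timed 25-foot walk, with proportions 0.6 and 0.3, two-sided 0.05 and 80% power. With pooled variance under the null and no continuity correction:

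n = [1.960 × √(2 × 0.45 × 0.55) + 0.842 × √(0.6 × 0.4 + 0.3 × 0.7)]² / 0.3² = (1.379 + 0.565)² / 0.09 ≈ 42 per arm.

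This reproduces the stated 42. It says nothing about RNFL, for which the documents give no effect, standard deviation or power.

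**2. What the cut-off covers.**
- For a Spectralis-only reading: the rule follows scan definitions tied to Spectralis protocol sets, and the eye-tracker named just after it is from the same maker. The fallback comes later, as an exception.
- For a universal reading: the rule applies to each scan, without qualification, and the fallback clause does not disapply it.

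The text does not decide between the two. Nor does it give a score range for any instrument, so the effect of a 20 elsewhere cannot be computed. As pure assumptions: on an index running from 0 to 10 every scan would fail, while on one running from 0 to 100 the limit would sit at one fifth of the range and might screen little.

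**3. Pooling.** If a subject changes system, the observed change is the true change plus an offset δ between systems. If a share s of subjects switch in the same direction, this adds δ² × s × (1 − s) to the variance of change. The documents give neither δ nor s, so no figure follows.

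**4. Illustration of scan loss.** Assume that a share f of subjects lose all scans, equally in both arms, and that the RNFL contrast would have 80% power with complete data.

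- Standard-error ratio = 1 / √(1 − f)
- Power = Φ(2.802 × √(1 − f) − 1.960), where 2.802 = 1.960 + 0.842
- Detectable effect in SD units at 80% power = 2.802 × √(2 / (m × (1 − f))), with m = 50 per arm randomized, or m = 40 after 20% dropout (the upper end of the range in 6.B)

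| f | SE ratio | Power | Detectable effect, m = 50 | Detectable effect, m = 40 |
|---|---|---|---|---|
| 0 | 1.000 | 80.0% | 0.56 | 0.63 |
| 10% | 1.054 | 75.7% | 0.59 | 0.66 |
| 20% | 1.118 | 70.7% | 0.63 | 0.70 |
| 33% | 1.225 | 62.8% | 0.69 | 0.77 |

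The 33% row corresponds to one of three equal-sized sites. The first row is what section 5.G expects.

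**The case against.** The strongest reply is that the fallback is a contingency the plan does not expect to use. Section 5.G expects the Spectralis glaucoma protocol at every site, so the expected loss is nil. That stands, and it limits the severity. It does not close the gap: the sponsor wrote the option in, and section 7.C allows sites to be added later.

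A second reply is that the placement which suggests a Spectralis cut-off also suggests that the 20 was never meant for another system, so nothing would be deleted by rule. That is a fair reading. It replaces a misapplied criterion with no criterion, and the remedy is the same.

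Third, the fallback depends on whether a site has the instrument, not on a choice made at each visit, and no switching is described. That stands too: the one-system rule is a safeguard against something possible, not a correction of something planned.

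A reader might infer that a site's valid scans would all be thrown out, or its poor ones all kept. The documents do not support this, because they give no score scale for any device and do not state that 20 is a Spectralis value. A reader might also infer a biased treatment comparison. Section 6.C stratifies 1:1 randomization by center. If each site keeps one system, loss or noise falls about equally on both arms, and the outcome is within-subject change. Lastly, the two statements on availability need not be a flat contradiction. They can be read as an expectation and a contingency, but they should be reconciled.

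**Conclusion.** The point holds as a minor one. The plan permits a second maker's OCT system without saying which quality criterion applies to it. It has no rule keeping a subject on one system, and no device or site term in the RNFL models.

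If the fallback is used, the likely cost is precision of a secondary endpoint. The size is unknown. It is nil with Spectralis at every site. Under the assumed total loss of scans in 10% to 33% of subjects, a contrast assumed to have 80% power falls to about 76% to 63%. Those figures rest on an assumed share, an assumed starting power and equal loss in both arms, and any endpoint losing that share of subjects would give the same numbers. They do not show that the RNFL endpoint will be damaged.

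**What to change.** - In section 5.G, limit the cut-off of 20 to Spectralis. For any other system, pre-specify a quality criterion on that instrument's own scale before unblinding. Section 6.D leaves the study statistician unblinded and section 7.G has efficacy analysed each year, so whoever sets the criterion should not have seen RNFL results by arm.
- Require all of a subject's scans to come from one system and one scan protocol.
- In section 6.E, add device to the RNFL models, or site, which is the randomization stratum and absorbs device if each site keeps one system.
- Reconcile the expectation that every site has the glaucoma protocol with the clause for sites that have no Spectralis.

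The cost is a few sentences and one model term, with no new scans. The downside is that a subject whose site changes device contributes scans from one system only.
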